1. AMENDMENTS FROM PREVIOUS VERSION(S)

This is an amendment to the original SAP.

[figure not shown]
2. INTRODUCTION

This document describes the planned statistical analyses for Protocol B0601002 Amendment 5, dated 16 August 2017. This statistical analysis plan (SAP) amendment is meant to supplement the study protocol. This SAP supersedes the statistical considerations identified in the protocol and, where considerations are substantially different they will be identified as such. Any deviations from this analysis plan will be described in the clinical study report (CSR). Any post-hoc, or unplanned analyses performed that are not specified in this SAP will be clearly identified in the CSR. This plan is developed and finalized prior to database lock of the clinical database. This SAP is written with consideration of the recommendations outlined in the International Conference on Harmonisation (ICH) E9 Guideline (Guidance for Industry: Statistical Principles for Clinical Trials) and on the ICH E3 Guideline (Guidance for Industry: Structure and Content of Clinical Study Reports).

2.1. Study Design

This is a Phase 1, open label, multi center, multiple dose, dose escalation, safety, pharmacokinetic, and pharmacodynamic study of PF 04518600 monotherapy in Part A, and PF 04518600 in combination with utomilumab in Part B. Each part includes a dose escalation phase, and a dose expansion phase. A maximum of approximately 210 patients are expected to be enrolled into the study.

Figure 1. Study Schematic

All patients will complete up to 4 weeks of screening. Following the initial dose(s), treatment with investigational product will continue until either disease progression by immune related response evaluation criteria in solid tumors (irRECIST), patient refusal, or unacceptable toxicity occurs, or end of study, whichever occurs first. Patients will be allowed to stay on study, if the treating physician feels that it is in the patient's best interest in the case of radiological progression, and the absence of clear clinical progression. A follow up visit approximately 4 weeks after the last dose for adverse event (AE) and serious AE (SAE) collection will be conducted. Late immune related adverse events will be evaluated up to 98 days after the first dose(s) of Cycle 1. Because atypical tumor responses after growth of preexisting lesions or appearance of new lesions have been observed with immune checkpoint inhibitors, study B0601002 will assess tumor response based on both response evaluation criteria in solid tumor (RECIST) and Immune related Response Criteria Derived From RECIST v1.1 (irRECIST). Survival data will also be collected.

Part A Monotherapy

Part A1 Monotherapy Dose Escalation

Part A1 monotherapy dose escalation phase will enroll approximately 58 adult patients with locally advanced or metastatic cancers hepatocellular carcinoma (HCC), melanoma, clear cell renal cell carcinoma (RCC) or head and neck squamous cell carcinoma (HNSCC). The actual number of patients enrolled will depend on the observed safety and tolerability profile of PF-04518600, the number of dose levels that will be tested and expanded to characterize the pharmacodynamic or immunomodulatory (IM) effects, and the number of dose levels required to identify the maximum tolerated dose (MTD) or optimal biological dose (OBD). Six dose levels are proposed: 0.01, 0.1, 0.3, 1.5, 3.0 and 10.0 mg/kg. Each cohort will include an initial cohort of 2-4 patients that may be expanded to approximately 10 patients. Approximately 3 patients enrolled in Japan will be included for at least 2 dose levels. A modified toxicity probability interval (mTPI) method,¹ targeting a dose limiting toxicities (DLT) rate of 25% and an acceptable DLT interval (20% 30%), will be utilized for dose escalation.

Part A2 Monotherapy Dose Expansion

Part A2 monotherapy dose expansion phase will randomize HCC patients 1:1 to flat dose levels of either 30 mg (Arm 1) or 250 mg (Arm 2) of PF 04518600 given every 2 weeks. Both doses were chosen based on data from Part A1. Each arm in Part A2 will include approximately 20 HCC patients.

Part B Combination Therapy

Part B1 Combination Therapy Dose Escalation

Part B1, the combination therapy dose escalation phase, will enroll approximately 53 patients. At least 6 patients must have been evaluated for the 28 day DLT observation period at the 0.3 mg/kg dose level in Part A1 PF-04518600 (OX40 agonist) monotherapy before Part B1 can be initiated. Part B1 will study sequential dose levels of PF-04518600 (0.1, 0.3, 1.0 and 3 mg/kg) combined with either 20 mg or 100 mg of

utomilumab (4-1BB agonist) in adult patients with non-small cell lung cancer (NSCLC), HNSCC, melanoma, bladder, gastric or cervical cancer who are unresponsive to currently available therapies or for whom no standard therapy is available. The starting dose level will be 0.1 mg/kg of PF-04518600 and 20 mg of utomilumab, given no sooner than 30 minutes apart.

A mTPI method, targeting a DLT rate of 25% and an acceptable DLT interval (20%-30%) will be utilized for dose escalation.

Part B2 Dose Expansion

Part B2 combination therapy dose expansion phase will further evaluate safety and anti-tumor activity of the combination of 30 mg PF-04518600 and 20 mg of utomilumab. Part B2 will be divided into 2 arms:

Arm 1 will enroll melanoma patients who have either:

- a. *Ocular melanoma; and have received no more than one line of systemic therapy for metastatic disease. Patients must not have received immune modifying agents (eg, anti-PD-L1, anti-PD1, anti-CTLA4, TNF agonist, etc.) for metastatic disease; or*
- b. *Cutaneous/acral melanoma; and have 1) only previously received systemic therapy for advanced/metastatic disease with the following therapies: BRAF and MEK inhibitors, anti-PD-L1, anti-PD-1, or anti-CTLA4 and 2) have received checkpoint inhibitor (anti-PD-L1, anti-PD-1, or anti-CTLA4) based treatment as most recent line of therapy on which disease progressed, as long as progression did not occur in the first 3 months of receiving checkpoint inhibitor treatment.*

Arm 2 will enroll NSCLC patients who have:

- a. *Previously received prior anti-PD-L1 or anti-PD-1 mAb as most recent therapy; and,*
- b. *did not have progressive disease as best overall response on recent PD-L1/PD-1 therapy (ie, stable disease ≥ 3 months, PR, or CR), and 3) who subsequently progressed on PD-L1/PD-1 therapy.*

2.2. Study Objectives

2.2.1. Objectives for Part A Monotherapy

2.2.1.1. Objectives for Part A1 Monotherapy Dose Escalation

[figure not shown]
Primary Objective:

- To assess safety, and tolerability at increasing dose levels of PF-04518600 in patients with selected advanced or metastatic solid tumors in order to establish the MTD.

Secondary Objectives:

- To assess preliminary anti-tumor clinical activity of PF-04518600 in patients with selected advanced or metastatic solid tumors.
- To characterize the single dose and multiple dose PK of PF-04518600 following IV administration.
- To evaluate the immunogenicity of PF-04518600 following IV administration.
- To characterize the degree of target engagement (TE) by PF-04518600 at multiple doses by measuring unbound (free) cell surface OX40 in peripheral blood.

CCI

2.2.1.2. Objectives for Part A2 Monotherapy Dose Expansion

Primary Objectives:

- To establish the RP2D of PF-04518600 in patients with selected advanced or metastatic HCC.
- To further characterize the safety and tolerability of PF-04518600 in patients with selected advanced or metastatic HCC.

Secondary Objectives:

1. To assess preliminary anti-tumor clinical activity of PF-04518600 in patients with selected advanced or metastatic HCC.

2. To characterize the single dose and multiple dose PK of PF-04518600 following IV administration.
3. To evaluate the immunogenicity of PF-04518600 following IV administration.

CCI

2.2.2. Objectives for Part B Combination Therapy

2.2.2.1. Objectives for Part B1 Combination Therapy Dose Escalation

Primary Objective:

- To assess safety and tolerability at increasing dose levels of PF-04518600 in combination with utomilumab in patients with selected advanced or metastatic solid tumors and to estimate MTD of the combination.

Secondary Objectives:

- To assess preliminary anti-tumor clinical activity of PF-04518600 in combination with utomilumab.
- To characterize single and multiple dose pharmacokinetics of PF-04518600 and utomilumab when given in combination.
- To evaluate immunogenicity of PF-04518600 and utomilumab when given in combination.

CCI

- [REDACTED]

2.2.2.2. Objectives for Part B2 Combination Therapy Dose Expansion

Primary Objective:

- To further assess safety and tolerability of PF-04518600 in combination with utomilumab in patients with melanoma or NSCLC in order to establish RP2D for the combination.

Secondary Objectives:

- To assess preliminary anti-tumor clinical activity of PF-04518600 in combination with utomilumab.
- To characterize single and multiple dose pharmacokinetics of PF-04518600 and utomilumab when given in combination.
- To evaluate immunogenicity of PF-04518600 and utomilumab when given in combination.

CCI

- [REDACTED]

2.3. Endpoints

2.3.1. Endpoints for Part A Monotherapy

2.3.1.1. Endpoints for Part A1 Monotherapy Dose Escalation

Primary Endpoints:

- Dose limiting toxicities (DLTs) observed in each patient during the first 98 days in order to determine the MTD.
- AEs as characterized by type, frequency, severity (as graded by NCI CTCAE v 4.03), timing, seriousness and relationship to study therapy PF-04518600.
- Laboratory abnormalities as characterized by type, frequency, severity (as graded by NCI CTCAE v. 4.03) and timing.

Secondary Endpoints:

- Objective tumor response, as assessed using the RECIST version 1.1 and irRECIST.

- Anti-tumor activity assessments of: PFS, TTP, SD, DR by RECIST version 1.1 and irRECIST and OS.

- Overall survival rates at 6 months, 1 year and 2 years.

- Pharmacokinetic parameters of PF-04518600:

Single Dose (SDo) - C_{\max} , $AUC_{sdo, \tau}$, AUC_{inf} , $t_{1/2}$, as data permit.

Multiple Dose (MD) (assuming steady-state is achieved) - $C_{ss,\max}$, $AUC_{ss,\tau}$, $t_{1/2}$, $C_{ss,\min}$, $C_{ss,av}$, CL, and V_{ss} , and R_{ac} ($AUC_{ss, \tau} / AUC_{sdo, \tau}$) as data permit

- Incidence of ADA and NAb against PF-04518600.

- Levels of free OX40 receptor expressed on T cells in peripheral blood.

CCI

2.3.1.2. Endpoints for Part A2 Monotherapy Dose Expansion

Primary Endpoints:

- AEs as characterized by type, frequency, severity (as graded by NCI CTCAE v 4.03), timing, seriousness and relationship to study therapy PF-04518600.
- Laboratory abnormalities as characterized by type, frequency, severity (as graded by NCI CTCAE v. 4.03) and timing.

Secondary Endpoints:

- Objective tumor response, as assessed using the RECIST version 1.1 and irRECIST.

- Anti-tumor activity assessments of: PFS, TTP, SD, DR by RECIST version 1.1 and irRECIST and OS.

- Overall survival rates at 6 months, 1 year and 2 years.

- Pharmacokinetic parameters of PF-04518600:

[figure not shown]
Single Dose (SDo) - C_{\max} , $AUC_{sdo, \tau}$, AUC_{inf} , $t_{1/2}$, as data permit.

Multiple Dose (MD) (assuming steady-state is achieved) - $C_{ss,\max}$, $AUC_{ss,\tau}$, $t_{1/2}$, $C_{ss,\min}$, $C_{ss,av}$, CL, and V_{ss} , and R_{ac} ($AUC_{ss, \tau} / AUC_{sdo, \tau}$) as data permit

- Incidence of ADA and NAb against PF-04518600.

CCI

- 
- 
- 
- 
- 
- 
- 

2.3.2. Endpoints for Part B Combination Therapy

2.3.2.1. Endpoints for Part B1 Combination Therapy Dose Escalation

Primary Endpoints:

- DLTs observed in each patient during the first 98 days in order to determine the MTD.
- AEs as characterized by type, frequency, severity (as graded by NCI CTCAE v 4.03), timing, seriousness and relationship to PF-04518600/utomilumab combination.

- Laboratory abnormalities as characterized by type, frequency, severity (as graded by NCI CTCAE v. 4.03) and timing.

Secondary Endpoints:

- Objective tumor response, as assessed using the RECIST version 1.1 and irRECIST.
- Anti-tumor activity assessments of: PFS, TTP, SD, DR by RECIST version 1.1 and irRECIST and OS.
- Overall survival rates at 6 months, 1 year and 2 years.
- Pharmacokinetic parameters of PF-04518600 and utomilumab:

Single Dose (SDo) - C_{max} , $AUC_{sdo, \tau}$, AUC_{inf} , $t_{1/2}$, as data permit.

Multiple Dose (MD) (assuming steady-state is achieved) - $C_{ss,max}$, $AUC_{ss,\tau}$, $t_{1/2}$, $C_{ss,min}$, $C_{ss,av}$, CL , and V_{ss} , and R_{ac} ($AUC_{ss,\tau} / AUC_{sdo,\tau}$) as data permit

- Incidence of ADA and NAb against PF-04518600 and utomilumab.

CCI

2.3.2.2. Endpoints for Part B2 Combination Therapy Dose Expansion

Primary Endpoints:

- AEs as characterized by type, frequency, severity (as graded by NCI CTCAE v 4.03), timing, seriousness and relationship to PF-04518600/utomilumab combination.
- Laboratory abnormalities as characterized by type, frequency, severity (as graded by NCI CTCAE v. 4.03) and timing.

Secondary Endpoints:

- Objective tumor response, as assessed using the RECIST version 1.1 and irRECIST.
- Anti-tumor activity assessments of: PFS, TTP, SD, DR by RECIST version 1.1 and irRECIST and OS.
- Overall survival rates at 6 months, 1 year and 2 year.
- Pharmacokinetic parameters of PF-04518600 and utomilumab:

Single Dose (SDo) - C_{max} , $AUC_{sdo, \tau}$, AUC_{inf} , $t_{1/2}$, as data permit.

Multiple Dose (MD) (assuming steady-state is achieved) - $C_{ss,max}$, $AUC_{ss,\tau}$, $t_{1/2}$, $C_{ss,min}$, $C_{ss,av}$, CL, and V_{ss} , and R_{ac} ($AUC_{ss, \tau} / AUC_{sdo, \tau}$) as data permit.

- Incidence of ADA and NAb against PF-04518600 and utomilumab.

CCI

3. INTERIM ANALYSES, FINAL ANALYSES AND UNBLINDING

There are no formal interim statistical analyses in this open label, unblinded clinical trial. During the conduction of the study, the Pfizer study team will review safety, immunogenicity, pharmacokinetics, pharmacodynamics, **CCI** and other data throughout the study.

Of the Bayesian mTPI procedure for assessing dose limiting toxicity, as the data arrive, it may become necessary to consider updating the Bayesian model and update the Bayesian Posterior Distribution.

Based on emerging data from Parts B1 and B2, if no response has been seen by the time the 10th patient enrolls in either arm in B2, enrollment may pause until a patient experiences a response or after the 16 week tumor assessment for the 10th patient, whichever is first. If at least 1 response does not occur in the first 10 patients in an arm, then enrollment may stop in that arm. Enrollment will continue in any arm that has at least 1 responder in the first 10 patients. If there are responders in both arms before the 10th patient enrolls, then enrollment will continue to the full 20 patients for each arm.

4. HYPOTHESES AND DECISION RULES

4.1. Statistical Hypotheses

This clinical trial implements a Bayesian procedure to determine the MTD. No classical hypothesis testing will be done. Decisions will be based on Bayesian posterior probabilities arising from a full hierarchical probability model.

4.2. Statistical decision rules

The initial Statistical Decision rules are described in the following table:

Table 1. Decision Rules

Number of Patients Having DLT	Number of Patients Treated at a Dose level										
	n=2	n=3	n=4	n=5	n=6	n=7	n=8	n=9	n=10	n=11	n=12
0	E	E	E	E	E	E	E	E	E	E	E
1	n/a	S	S	S	E	E	E	E	E	E	E
2	U	D	D	S	S	S	S	S	S	S	S
3		U	U	D	D	S	S	S	S	S	S
4			U	U	U	D	D	D	D	D	S
5				U	U	U	U	U	D	D	D
6					U	U	U	U	U	U	D
7						U	U	U	U	U	U

D: De-escalate the dose; E: Escalate the dose; S: Stay at the dose;
U: Unacceptable toxicity;
n/a: Not applicable

5. ANALYSIS SETS

5.1. Full Analysis Set

The Full Analysis Set (FAS) is defined as all enrolled patients who receive at least one full or partial IV infusion of study drug PF-04518600.

5.2. 'PER PROTOCOL' Analysis Set evaluable for MTD

The per protocol analysis set includes all enrolled patients who receive at least two cycles of study medication and who do not have major treatment deviations during first two cycles.

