#### 5. STUDY TREATMENTS

For the purposes of this study, and per International Conference on Harmonization (ICH) guidelines investigational product is defined as a pharmaceutical form of an active ingredient or placebo being tested or used as a reference in a clinical trial, including a product with a marketing authorization when used or assembled (formulated or packaged) in a way different from the approved form, or when used for an unapproved indication, or when used to gain further information about an approved use (ICH E6 1.33). Eligible patients will be enrolled to receive PF-04518600 (and utomilumab for Part B patients) in an open-labeled, unblinded manner. Patients will be registered and successively assigned to the next available treatment slot at a dose level or dose combination level decided on after the previous cohort's safety evaluation and ongoing observations of earlier enrolled patients. For monotherapy, patients will be dosed at 0.01 mg/kg PF-04518600 in the first cohort. For combination therapy, patients will be dosed at 0.1 mg/kg PF-04518600 and 20 mg utomilumab in the first dose combination level. Selected dose for PF-04518600 in the B2 combination therapy dose expansion cohorts is 30 mg (a flat dose equivalent to 0.3 mg/kg) intravenously (IV) Q2W in combination with PF-05082566 20 mg IV every 28 days.

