#### 5.4.4. Part B2 Combination Therapy

In Part B2, utomilumab will be administered on Day 1 of every other cycle (every 28 days) per IP Manual as an intravenous (IV) infusion over 60 minutes (-5 to +15 minutes and should include the time needed to flush the infusion line). Utomilumab will be administrated intravenously using a flat dose.

PF-04518600 will be administered intravenously as a flat dose on Day 1 of each 2 week cycle per the IP Manual as an intravenous (IV) infusion over 60 minutes (-5 to +15 minutes and should include the time needed to flush the infusion line). On cycles whereby both PF-04518600 and utomilumab are to be administered on the same day, PF-04518600 will be administered after, but no sooner than 30 minutes after completion of the utomilumab infusion in absence of infusion reaction and after post-utomilumab and pre- PF-04518600 pharmacokinetic blood draws (see Section 5.4.5.6.2 Dose Reductions, Interruptions, and Discontinuation Criteria Part B Combination). All blood draws should be

taken from the contra-lateral arm of the infusion. Furthermore, separate infusion bags, infusion lines, and filters must be used for each investigational product. Indwelling catheters should be flushed prior to infusion of each investigational product.

A cycle is defined as the time from Day 1 dose of PF-04518600 to the next Day 1 dose. If there are no treatment delays, a cycle will be 2 weeks. Each patient may receive PF-04518600 and utomilumab until disease progression by irRECIST (see Section 5.4.6 Treatment After Initial Evidence of Radiological Progression), intolerability, death, or until end of study, whichever comes first.

If infusion reaction occurs, refer to Section 5.4.5.1 Infusion Reactions and Appendix 4 for management of infusion reactions. If premedication is required for the management of infusion reactions, administration of PF-04518600 not sooner than 30 minutes before utomilumab administration may be considered.

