### 9. DATA ANALYSIS/STATISTICAL METHODS

## 9.1. Analysis Sets

a. Safety analysis set.

The safety analysis set includes all enrolled patients who receive at least one dose of study medication.

b. Full analysis set.

The full analysis set includes all enrolled patients.

c. Per protocol analysis set (evaluable for MTD).

The per protocol analysis set includes all enrolled patients who receive at least one dose of study medication and who do not have major treatment deviations during first cycle. Patients with major treatment deviations in DLT observation period are not evaluable for the MTD assessment and will be replaced as needed to permit MTD estimation. Major treatment deviations include:

- Administration of less than 75% of the planned dose of PF-04518600 provided that the reduction is not due to toxicity attributable to PF-04518600.
- Administration of more than 150% of the planned dose of PF-04518600.
- d. PK analysis sets.

The PK parameter analysis population is defined as all enrolled patients treated who have sufficient information to estimate at least 1 of the PK parameters of interest.

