# Hypersensitivity reactions:

- 1. NCI-CTCAE Grade 1 allergic reaction or cytokine release syndrome.
  - Monitor for worsening condition. If the reaction worsens, stop the infusion. Institute premedication for subsequent infusions as per Section 5.4.5.5 Dose Delay.
- 2. NCI-CTCAE Grade 2 allergic reaction or cytokine release syndrome.
  - Stop PF-04518600 or PF-05082566 infusion.
  - Administer bronchodilators, oxygen, acetaminophen, etc. as medically indicated.
  - Resume infusion at 50% of previous rate once reaction has decreased to Grade 1 in severity. Monitor closely for any worsening. If the reaction recurs, stop infusion. Institute premedication for subsequent infusions as per Section 5.4.5.5 Dose Delay.
- 3. NCI-CTCAE Grade 3 or Grade 4 allergic reaction or cytokine release syndrome or anaphylaxis.
  - A Grade 3 anaphylaxis (hypersensitivity reaction) consists of symptomatic bronchospasm requiring parenteral medications with or without urticaria, allergy-related edema/angioedema, or hypotension.
  - A Grade 4 anaphylaxis (hypersensitivity reaction) is a life-threatening event requiring urgent intervention.
- 4. Treatment of Grade 3 or Grade 4 allergic reaction, cytokine release syndrome or anaphylaxis.
  - Stop the PF-04518600 or PF-05082566 infusion immediately and disconnect infusion tubing from the patient.

- Administer epinephrine, bronchodilators, antihistamines, glucocorticoids, intravenous fluids, vasopressor agents, oxygen, etc. as medically indicated.
- Telephone Sponsor or designated representative to report an SAE as per Section 8 Adverse Event Reporting.
- For a NCI-CTCAE Grade 3 or 4 hypersensitivity reaction, study treatment will be discontinued.
- 5. Re-treatment following Grade 1 or Grade 2 allergic reactions or cytokine release syndrome.
  - Once the PF-04518600 or PF-05082566 infusion rate has been decreased due to an allergic reaction or cytokine release syndrome, it will remain decreased for all subsequent infusions.
  - If the patient has a second reaction at the lower infusion rate, the infusion should be stopped and the patient should receive no further PF-04518600 or PF-04518600/PF-05082566.
  - If the patient experiences a Grade 3 or 4 allergic reaction, cytokine release syndrome, or anaphylaxis at any time, the patient should receive no further PF-04518600 or PF-04518600/PF-05082566.

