5.3. Safety Analysis Set

The Safety Analysis Set is the same as the Full Analysis Set.

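### SAP 5.1 and 5.3 admit only patients infused with PF-04518600, so a Part B patient who receives utomilumab alone is missing from the primary adverse event analysis

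*SAP*

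**What the plan says.** SAP 5.1 defines the Full Analysis Set (FAS) as "all enrolled patients who receive at least one full or partial IV infusion of study drug PF-04518600". SAP 5.3 adds: "The Safety Analysis Set is the same as the Full Analysis Set". Protocol 9.1 keeps two different sets: "The safety analysis set includes all enrolled patients who receive at least one dose of study medication", and "The full analysis set includes all enrolled patients". SAP section 2 settles which governs: "This SAP supersedes the statistical considerations identified in the protocol and, where considerations are substantially different they will be identified as such".

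Part B patients receive two investigational products (Protocol 5). On days when both are due, Protocol 5.4.3 and 5.4.4 give utomilumab first. PF-04518600 follows "no sooner than 30 minutes after completion of the utomilumab infusion in absence of infusion reaction". Under Protocol 5.4.5.6.2 the second agent is held after a reaction to the first until symptoms have cleared, and the two agents must be stopped together. Appendix 4 states: "For a NCI-CTCAE Grade 3 or 4 hypersensitivity reaction, study treatment will be discontinued". It also ends treatment if a second reaction occurs at the reduced infusion rate.

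SAP 7.2.1 runs the primary analysis, including adverse event incidence, on the FAS. SAP 7.2.3 uses the FAS for patient accounting, and the Safety set for adverse events, laboratory abnormalities, baseline characteristics, treatment administration and discontinuations.

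**The concern.** The SAP definition suits monotherapy, where PF-04518600 is the only study drug. In Part B it ignores the drug that is given first. A patient can be exposed to study medication, react to it, be taken off treatment for that reason, and then not meet the condition for being counted.

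Adverse events and laboratory abnormalities are primary endpoints in all four parts. The omission depends on the outcome, because the reaction is what prevents the qualifying infusion. Protocol 3.3 treats reactions of this kind as important in very small numbers: one Grade 4 cytokine release, infusion or allergic reaction among 6 patients puts a dose level above the MTD.

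There is a smaller, separate matter in Part A2. Patients are randomised there, and treatment may start up to four days after registration. A patient can therefore be randomised and never infused.

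**Working it through.** The plan gives no figure to reproduce. The check applies both sets of definitions to the two patient types, traces the tables affected, and then sizes the effect.

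**1. Set membership**

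| Patient | Protocol Safety | Protocol full set | SAP Safety | SAP FAS |
|---|---|---|---|---|
| Part B, utomilumab only | yes | yes | no | no |
| Part A2, randomised, never treated | no | yes | no | no |

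**2. When a Part B patient is lost.** All of these must hold: utomilumab is given first on Cycle 1 Day 1, treatment stops, and PF-04518600 is never started. A reaction that resolves and is followed by PF-04518600 keeps the patient in. So does a utomilumab reaction at Cycle 3 or later, because PF-04518600 has already been given. So does any reaction during PF-04518600, because a partial infusion qualifies.

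**3. Tables affected.** By the SAP's own wording: the primary adverse event analysis (FAS); the adverse event, laboratory, baseline, exposure and discontinuation tables (Safety set); and patient accounting (FAS). SAP 7.2.7 also counts antibody-positive patients in the safety population. The SAP names no set for the ECG, cytokine release, echocardiogram/MUGA and liver-injury tables. Protocol 9.6 assigns safety summaries to the Safety set.

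**4. Size of the effect.** Suppose k of n patients have the event and one of those k is omitted. The reported rate becomes (k − 1)/(n − 1), which cannot exceed k/n because k ≤ n. For a B2 arm of 20 in which only the omitted patients had the event (exact Clopper-Pearson 95% intervals):

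| Utomilumab-only reactors | Any study medication | SAP set |
|---|---|---|
| 1 | 1/20 = 5.0% (0.1% to 24.9%) | 0/19 = 0% (0% to 17.6%) |
| 2 | 2/20 = 10.0% (1.2% to 31.7%) | 0/18 = 0% (0% to 18.5%) |

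In a B1 dose level expanded to 10, one such patient turns 1/10 = 10% into 0/9.

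**5. How likely is at least one such patient?** The documents give no rate, so the per-patient rate p is an assumption. Part B plans up to 55 patients in B1 and about 40 in B2 (Protocol 9.3.2), 95 in all. The chance of at least one is 1 − (1 − p)^95, and the expected number is 95p.

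| p (assumed) | Expected | Chance of at least one |
|---|---|---|
| 0.5% | 0.475 | 37.9% |
| 1% | 0.95 | 61.5% |
| 2% | 1.9 | 85.3% |
| 5% | 4.75 | 99.2% |

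**6. Part A2 accounting.** For 40 patients the chance of at least one randomised but untreated is 1 − (1 − p)^40. This is 33.1%, 55.4% and 87.1% at assumed rates of 1%, 2% and 5%.

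**The case against.** The strongest reply is that the gap is narrow and the consequences limited. Much of that stands.

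- **Rarity.** The protocol's background covers 167 utomilumab patients and reports no DLTs. The one serious infusion reaction it describes was attributed to rituximab. Patients with a severe earlier reaction to antibodies are excluded at entry. If this is read as 0 in 167 for a severe utomilumab reaction, the one-sided 95% upper limit is 1 − 0.05^(1/167) = 1.8%. The 5% row above is then unlikely for severe reactions. Infusion order may also be reversed when premedication is needed.
- **Safety decisions.** Grade 3 or higher infusion and allergic reactions that are clinically significant are DLTs under Protocol 3.2. Protocol 3.3 has its own rule for such reactions, and serious event reporting covers any investigational product from consent. None of this runs through the FAS or Safety set. A reader might infer that dose escalation is compromised; the documents do not support that. The set evaluable for the MTD is defined separately and is not part of this point.
- **Scope.** A reader might infer that the patient drops out of every safety table. The SAP does not say so: four groups of tables have no named set. Only Protocol 9.6 combined with the SAP definition reaches them.
- **Severity.** A reader might infer that the rule removes exactly the worst reactions to the combination. It does not. The lost patient received utomilumab alone, and the event need not be Grade 3 or 4, since repeated milder reactions or a refusal could also end treatment.
- **Part A2.** Leaving untreated patients out of safety tables is normal and agrees with Protocol 9.1. Only the accounting is affected.
- **Intent.** The content of SAP section 1 is not shown, so it cannot be said that the change was undeclared or unexplained.

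SAP 5.6.2 plans a review of significant deviations, with decisions for each population, before database closure. That does not help: a patient managed according to protocol after a reaction has not deviated, and still fails the SAP definition.

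**Conclusion.** The point holds in limited form. Followed as written, the SAP omits a dosed Part B patient from a primary endpoint analysis and from the main safety tables, contrary to Protocol 9.1. For the event that led to the omission, the error runs one way, towards understated toxicity. With one such patient in a B2 arm of 20, the event is reported as 0/19 rather than 1/20, a loss of 5 percentage points. Events that the patient did not have would be slightly overstated by the smaller denominator.

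The number of such patients is unknown and probably small; the chances shown rest on assumed rates. The effect is confined to the reported tables. In Part A2 the effect is on patient accounting alone. The restriction looks like a monotherapy definition carried into Part B, though the documents do not state the reason. It is worth correcting before database lock because it touches a primary endpoint and costs almost nothing to change.

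**What to change.** Four edits to the SAP:

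1. **SAP 5.3.** Define the Safety set as every enrolled patient given all or part of an infusion of either product, PF-04518600 or utomilumab.
2. **SAP 5.1.** Restore the protocol's full set (everyone enrolled; for Part A2, everyone randomised) and use it for patient accounting.
3. **SAP 7.2.1.** Base the adverse event and laboratory summaries on the Safety set. Without this, edit 2 would put untreated patients in the denominators. Name the Safety set for the ECG, cytokine release, echocardiogram/MUGA and liver tables at the same time.
4. **SAP 5.5 and 7.1.** State that a Part B patient who received only utomilumab is summarised under the assigned dose-combination level. SAP 5.5 now places patients by actual treated dose, and SAP 7.1 by initial dose of study drug. A patient with no PF-04518600 dose has no clear cohort under either.

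The cost is a few sentences. No new data are needed, and no treatment or dosing rule changes.
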